#### **Secondary Outcome Measure 1 - Changes from baseline on the Overall Assessment of Speakers Experience of Stuttering (OASES)**

The OASES is a standardized assessment of the functional impact of stuttering on a person's life. There are 4 sub-tests: general information about speech, your reactions to stuttering, communication in daily situations, quality of life. Each one has a score from 1 to 5 with regard to impact (1 least, 5 most negative impact). These are combined to give a total impact score between 1 and 5, with 5 representing the highest negative impact on person's life. The change on the total impact score will be used.

#### **Other (Exploratory) Outcome Measures**

##### **1. Changes from baseline on rhythm judgement task**

Investigators will compare performance accuracy on a computerized rhythm judgement task from before and after tDCS to assess effects of tDCS. Improved accuracy reflects better performance.

## **2. Changes from baseline on tapping tasks**

Investigators will compare performance (variability and accuracy) on computerized tapping tasks from before and after tDCS to assess effects of tDCS. Decreased variability and improved accuracy reflect better performance.

## **3. Changes from baseline on self-rated measure of speech fluency**

Investigators will compare participant scores on a self-rated measure of speech fluency (1 = NO STUTTERING; 9 = EXTREMELY SEVERE STUTTERING) from before and after tDCS to assess effects of tDCS. Lower scores indicate improvement.

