### 1. Specific Aims

- 1.1. Specific Aim #1: Determine effects of anodal HD-tDCS targeting left pSTG on speech fluency in adults who stutter.** Pre-training measures of stuttering severity (e.g., percent stuttering-like disfluencies, OASES scores) will be compared with those same measures immediately following training, as well as 4 weeks post-training. We hypothesize that when paired with a fluency-inducing speech condition, active stimulation targeting left pSTG will lead to a greater increase in speech fluency compared to behavioral training alone (sham stimulation).
- 1.2. Specific Aim #2: Determine effects of anodal HD-tDCS targeting left pSTG on performance on rhythm judgement tasks.** Pre-training measures of performance (reaction time and accuracy) on finger-tapping tasks and rhythm judgment tasks will be compared with those same measures immediately following training, as well as 4 weeks post-training. We hypothesize that when paired with a fluency-inducing speech condition, active stimulation targeting left pSTG will lead to a greater increase in performance on these tasks compared to behavioral training alone (sham stimulation).
- 1.3. Specific Aim #3: Determine effects of anodal HD-tDCS targeting left pSTG on functional connectivity within BGTC regions during speech production.** Pre-training measures of functional connectivity within BGTC regions will be compared before and immediately following training, as well as 4 weeks post-training. We hypothesize that when paired with intensive training under fluency inducing conditions, active stimulation targeting left pSTG will lead to increased functional connectivity within the BGTC network compared to behavioral training alone (sham stimulation).

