#### **4.5. Separate sub study for healthy controls only**

We will also recruit approximately 50 adults who do not stutter to participate in a sub study to examine the effects of repeated training on the rhythm tasks (section 3.7). We need people who do not stutter to complete these tasks to get more information about the tasks. To get this information, we'd like 50 people between the ages of 18-65 years who do not stutter to perform the same tasks. This will be done on a computer and/or iPad. These tasks will involve listening to rhythms and making judgments about them, as well as performing some finger tapping exercises. Participants will complete these tasks 3 times: 1) the initial visit, 2) 5 days later, and 3) 4 weeks after visit 2. During their first visit, we may also administer brief speech and language tests, which involve looking at some pictures and answering questions about them, and a short working memory test. We will also ask them about musical training history. Therefore, the first visit will take approximately 2 hours, and visits 2 and 3 will take approximately 1 hour. These participants will only complete the speech assessment, musical training history, operation span, and rhythm tasks. They will not receive HD-tDCS or an MRI. They will complete the rhythm tasks three times: 1) initial visit, 2) 5 days later, and 3) 4 weeks after visit 2. This is to mimic the testing procedure of the adults who stutter.

The only exclusion criteria would be history of stuttering or other speech, language, memory, cognitive, or psychiatric disorders.

These subjects will receive \$50 for participating in this study via check in the mail. Additionally, if they complete the 1 month follow up (visit 3), they will receive a \$25 bonus.

They will sign a separate consent form. To keep their information confidential, we will label the survey and tests with a code, rather than their name or any other details that someone could use to identify them. Although we'll keep a list of all the people who answered our survey, no one outside our study team will be able to figure out who answered the survey or which people gave which answers. Completion of these tests won't benefit them directly. We hope what we learn will help other people in the future. The only risks include mild discomfort involved in completing the tests.

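### Section 3.10 sets out three exploratory outcomes as before-versus-after comparisons and names no active-versus-sham contrast, which for rhythm and tapping does not match Specific Aim 2

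*Combined protocol and SAP*

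**What the plan says.** Section 3.10 (Data analysis) lists three exploratory outcomes, each headed as a change from baseline.

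- Rhythm judgement: "Investigators will compare performance accuracy on a computerized rhythm judgement task from before and after tDCS to assess effects of tDCS".
- Tapping: "Investigators will compare performance (variability and accuracy) on computerized tapping tasks from before and after tDCS to assess effects of tDCS".
- Self-rated fluency, on a scale from 1 to 9 whose upper anchor and comparison read: "EXTREMELY SEVERE STUTTERING) from before and after tDCS to assess effects of tDCS. Lower scores indicate improvement".

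None of the three entries mentions the sham group. Both primary outcomes in the same section do: the fMRI entry expects larger change with active stimulation than with training plus sham, and the %SLD entry expects a larger fall in the active group than in the sham group.

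Elsewhere, Specific Aim 2 covers the tapping and rhythm tasks and states its hypothesis as "active stimulation targeting left pSTG will lead to a greater increase in performance on these tasks compared to behavioral training alone (sham stimulation"). Section 3.6 describes the whole project as between-subjects, sham-controlled and double-blinded. Section 4.5 recruits about 50 adults who do not stutter "to participate in a sub study to examine the effects of repeated training on the rhythm tasks".

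**The concern.** A before-after difference among stimulated participants mixes any stimulation effect with everything else that changes over the same period. The documents themselves point to several such components. Both arms read chorally during all five sessions (section 3.8). The %SLD entry anticipates improvement in both groups. The rhythm tasks are repeated, and section 4.5 treats repetition as worth studying. Baseline behavioural testing is at Visit 2, with no scan or stimulation that day, whereas the post-training tests share Visit 7 with a tDCS session and an MRI (section 3.6). A self-rating can also move with expectation in either arm.

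The sham arm is there to remove these shared components, but it does so only if the analysis uses it. If the three entries are applied as worded, a change that would have occurred under sham is reported as an effect of tDCS. For rhythm and tapping, the section would then answer a different question from the one Specific Aim 2 asks.

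**Working it through.** **1. Where a sham contrast is stated**

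| Outcome | Section 3.10 names active vs sham? | Stated elsewhere? |
|---|---|---|
| fMRI (primary 1) | Yes | Aim 3, for functional connectivity |
| %SLD (primary 2) | Yes | Aim 1, %SLD given as an example |
| OASES (secondary) | No, change in total score only | Aim 1, OASES given as an example |
| Rhythm judgement | No | Aim 2, by name |
| Tapping | No | Aim 2, by name |
| Self-rating 1-9 | No | Not by name |

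For rhythm and tapping, Aim 2 begins "Pre-training measures of performance (reaction time and accuracy) on finger-tapping tasks and rhythm judgment tasks will be compared with those same measures" and then states the active-versus-sham hypothesis, so the defect is that section 3.10 does not carry that contrast over. For the self-rating the nearest text is Aim 1, which hypothesises that "active stimulation targeting left pSTG will lead to a greater increase in speech fluency compared to behavioral training alone (sham stimulation") but introduces its measures with "Pre-training measures of stuttering severity (e.g., percent stuttering-like disfluencies, OASES scores) will be compared with those same measures immediately following training". The self-rating is not listed there, so its contrast can at most be inferred.

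**2. Size of the problem if the wording is followed literally**

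The plan gives no figure to reproduce: no test, significance level, effect size, SD or allocation ratio is stated for any outcome. The only input from the documents is the target of 24 completers (section 4.1). Assumptions: 1:1 allocation, so 24 / 2 = 12 active participants; a paired t-test at two-sided 5%; no stimulation effect; and a shared change of d SDs of the within-person change score.

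The paired statistic follows a noncentral t with 12 - 1 = 11 degrees of freedom and noncentrality d × √12. The chance of declaring an effect is the probability that |t| exceeds the 5% critical value of 2.201.

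| d | d × √12 | Chance of a false tDCS effect |
|---|---|---|
| 0.2 | 0.693 | 10% |
| 0.3 | 1.039 | 16% |
| 0.5 | 1.732 | 35% |
| 0.8 | 2.771 | 71% |
| 1.0 | 3.464 | 88% |

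**3. The same situation with the sham arm used**

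Compare mean change between 12 active and 12 sham participants (two-sample t, 22 degrees of freedom). The noncentrality is δ × √(12/2), where δ is the between-arm difference in SDs of change. A change of size d in both arms cancels, so δ = 0 and the false-positive rate is 5% for every d in the table.

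**4. What the contrast can detect**

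Under the same assumptions, power is 22% for δ = 0.5 and 47% for δ = 0.8, and 80% power needs δ of about 1.20. The contrast is valid but imprecise at this sample size, which is a reason to report an interval.

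**The case against.** The best defence is that these three entries are outcome definitions, not analysis rules. Their headings speak of changes from baseline, they mainly say what is measured and which direction is better, and a change score is a natural input to a between-arm comparison. The OASES entry is equally silent on arms although Aim 1 plainly intends a sham comparison. No section prescribes a paired, within-arm or pooled test. The design is randomised and sham-controlled, and the outcomes are labelled exploratory.

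Much of this stands, and it rules out several stronger readings that a reader might infer:

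- That the trial has no sham contrast for any of the three outcomes. Aim 2 states one for rhythm and tapping.
- That Aim 2 has no analysis at all. The aim itself gives measures, time points and contrast; what is missing is agreement with section 3.10.
- That the plan commits to crediting shared change to stimulation. That follows only from a literal reading, since no model is given.
- That the self-rating is unblinded. Section 3.6 says double-blinded, and section 3.8 gives the sham arm the same 30-second ramp-up. The concern is that expectation can shift a subjective rating in both arms.
- That the error could be judged by a paired test on all 24 participants (29%, 65% and 96% at 0.3, 0.5 and 0.8 SD). That would pool sham participants as if stimulated, which no section proposes.

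What the defence does not remove is the wording. Each entry says that the pre-to-post comparison is what assesses tDCS, while the primary-outcome entries in the same section name the arms. The control sub-study does not fill the gap: it is non-randomised, in people who do not stutter, with neither sham nor choral reading, and it does not concern the self-rating.

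**Conclusion.** The point holds as a gap and an inconsistency in section 3.10. Three exploratory outcomes are given a before-after comparison as the assessment of tDCS, with no sham contrast. For rhythm and tapping this conflicts with Specific Aim 2; for the self-rating the contrast is not named anywhere.

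Read literally, the false-attribution rate is 16%, 35% or 71% for a shared change of 0.3, 0.5 or 0.8 SD, instead of 5%. The paired 5% test, 12 active participants and the size of the shared change are assumptions, so these figures illustrate the risk and do not predict it. The primary outcomes are unaffected because their text names the sham comparison. The consequence is confined to the exploratory claims, but these include both task types under Specific Aim 2, so the wording is worth correcting.

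**What to change.** In exploratory outcomes 1 to 3 of section 3.10, replace the before-after sentence with wording such as: The effect of tDCS is the active-minus-sham difference in the post-training score and in the 4-week score, each adjusted for the participant's own pre-training score, with a 95% confidence interval. Within-arm changes from baseline are descriptive only and are not attributed to tDCS.

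For rhythm and tapping the time points are Visit 7 and Visit 10, already scheduled in section 3.6. For the self-rating, apply the rule at whichever pre- and post-training visits it is collected, and name those visits: section 3.5 mentions self-ratings of speech and stuttering, but no section schedules the 1-9 scale. An unadjusted between-arm comparison of change would also cure the defect; baseline adjustment is preferred because it usually gives a tighter interval.

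The cost is about one sentence per outcome, with no new participants or procedures.

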## **4. Protection of Human Subjects**

### **4.1. Risks to Human Subjects**

#### **Human Subjects Involvement, Characteristics, and Design**

The proposed study will involve healthy adult participants between 18-65 years of age. All participants in the tDCS arm will be those who have been diagnosed with developmental stuttering. Although women are underrepresented in samples of adults with stuttering, we will make every effort to include women in the proportion they occur in the population with this disorder. While the ratio is closer in childhood, approximately 3 males to 1 female, in adults the ratio is approximately 5 males to 1 female. We will gather information on each participant's medical, social, and developmental history, and speech, language, and hearing background. In addition, stuttering participants will be audio-video recorded to obtain speech samples during conversation and reading. These will be used to determine their stuttering severity level using the standardized assessment, stuttering severity instrument (SSI-4; Riley 2009). Two trained speech-language pathologists experienced in disfluency analysis will independently score the SSI form to establish reliability of measurement. Participants will be randomly assigned to one of the two groups (active vs. sham stimulation).

In order to reach our target of 24 eligible adults who stutter who complete the study, and 50 eligible controls to participate in the rhythm tasks sub study only (see section 4.5 below), we will consent up to 200 people during the oral phone screening. It is possible that some participants who pass this screening may still become ineligible during the first visit, for example due to scoring below normal on the standardized tests, or having a stuttering score that is too low.

#### **Sources of Materials.**

This project involves *four sources* of research material: (1) *Questionnaire data* (e.g., Intake screening form, developmental history, demographic information, etc.), (2) *Brain imaging data* (e.g., high resolution structural image (MPRAGE), functional MRI), (3) *Audio-video recorded data* (e.g., audio-videotaping in a laboratory setting to sample speech), and (4) *Behaviorally coded data* (e.g., during testing, some behavioral observations will be coded by either paper-and-pencil means and/or subsequently through the use of computerized software e.g., frequency of stuttering-like disfluencies per task and/or during conversation, hearing screening data). All such data, whether in DVD, video, or paper format, will be stored in a locked filing cabinet in a locked storage room in the Rachel Upjohn Building at the U of M East medical campus, accessible only to the applicant and her mentorship team, and their students and staff. Once computerized data have been coded, organized and statistically analyzed, they will be stored in a password-protected computer housed in [name] lab. All computerized data files will contain only participants' non-identifying code numbers.

### **4.2. Potential Risks.**

**Breach of privacy.** The risks involving breach of sensitive private information will be minimized by having all participants' data de-identified and handled only by [name] and other authorized investigators. All subject data will be placed in individual coded files that will be locked in a cabinet in [name] office or lab.

**Inconvenience or discomfort during behavioral testing.** All participants will be given breaks as needed, and will not be pressured to continue if there is excessive anxiety or fatigue.

**Inconvenience or discomfort during HD-tDCS.** Any level of discomfort will be monitored very closely by an investigator that will be sitting beside the participants at all times during the experiment. If discomfort is noticeable/bothersome, we will discontinue the procedures immediately. In our experience (combined at UM and [name] doctoral research institution) we had no participants expressing discomfort that required termination of the study. Most complaints, if any, involved a "tingling", "itchy" sensation, rather than pain. There is only a minor risk of discomfort with HD-tDCS. Some people have reported slight itching or tingling sensation below the electrodes with HD-tDCS. A less common side effect is temporary skin redness and mild headache. Although adverse side effects such as seizures are possible, the procedure has been used safely without any reports of such adverse effects. Increased risk of skin burns and infection as a result of a single session of stimulation using conventional tDCS has been reported (Wang, Wei, Wen, & Li, 2014). However, in our study we will be using HD-tDCS rather than conventional tDCS. To date, there have been no reports of burns with high definition tDCS (Brunoni et al., 2011; Brunoni et al., 2012) and participants will be closely monitored throughout the study. If participants have a skin injury such as cuts or scrapes on their skin before participating in the study, they will not be eligible to participate as it will increase the likelihood of skin irritation. Additionally, headaches during and after stimulation may occur. It is unknown if HD-tDCS can pose a risk to fetuses. Also, to minimize other potential risks of tDCS, we will ask that participants fill out a side effects questionnaire after the stimulation. On the questionnaire, there will be a list of potential symptoms participants may experience. Participants are to check a box that best describes the symptom(s) they may be experiencing. The description of the symptoms range from Absent to Severe. Participants will also be asked to best describe the relationship between HD-tDCS and their symptoms. For a recently published comprehensive review of safety related to tDCS, please refer to Bikson et al. (2016).

The researchers will try to minimize these risks. We will be monitoring the subjects closely during the procedure. For all studies, we will use saline electrode gel to minimize the itching experienced. We will also slowly ramp up the current to the desired, low stimulation intensity. We will not exceed the stimulation intensities (2 mA) and durations (maximum of 20 min) that are known to be safe and closely monitor the condition of the skin throughout each session. We will monitor the condition of the skin to avoid significant discomfort. We will also ask the subjects questions about the subject's medical history to ensure the subject do not have any additional risk factors (e.g., a history of epilepsy) for a seizure prior to participating in this study. For women, the subject will be asked during screening whether she is pregnant or are trying to become pregnant; they should not take part in this study if they are. Sexually-active women of child-bearing potential are asked to use a reliable birth control method for the duration of this study. Also, to minimize other potential risks of tDCS, we will ask that the subject fill out a side effects questionnaire after the tDCS stimulation. On the questionnaire, there will be a list of potential symptoms the subject may experience. They are to check a box that best describes the symptom(s) They may be experiencing. The description of the symptoms range from Absent to Severe. They will also be asked to best describe the relationship between tDCS and the symptoms.

**Inconvenience or discomfort during MRI scanning.** Well-known risks for MRI scanning involve the presence of ferromagnetic foreign objects in and/or on the body (e.g., pacemaker, surgical clip, staples, etc.), claustrophobia, as well as possible inconvenience or discomfort during the scanning due to the requirement of lying still, and exposure to loud noise. The risks involved in MRI participation are usually greatly minimized through a thorough screening procedure performed by [name] as well as the fMRI Research Lab staff, followed by ample opportunity for exposure to the sights and sounds of the MRI setting, as well as the option to participate in a desensitization session in a mock MRI. Discomfort due to loud noise during scanning will be minimized through use of earplugs, headphones, and padding around the head as well as the inside of the MRI bore. If a participant shows any signs of discomfort or anxiety during the scanning, the procedure will be interrupted and stopped if necessary.

There is a minor risk of discomfort or anxiety from being in the confined space of the MRI scanner. The MRI scanner makes loud, vibrating noises. Some studies, like this one, have the potential to cause "peripheral nerve stimulation" (PNS). PNS is a light touching sensation on the skin surface, lasting only for a few seconds. There is also a risk that the magnetic fields could disturb a metal fragment in the body, interfere with an implanted device, such as a pacemaker or neurostimulator, or cause metal (including foil-backed medication patches) on or in the

body to heat up, causing the subject harm. Sometimes, subjects report a temporary, slight dizziness, light-headedness or nausea during or immediately after the scanning session.

To minimize these risks and discomfort, we will provide pads and blankets to make the subject as comfortable as possible. The subject will be able to talk to us throughout the study, and will be able let us know right away if they want to stop the study and get out of the scanner. They will wear foam earplugs to reduce the loud noises made by the scanner and prevent any hearing damage. It may cause mild discomfort, but is not harmful to them. The MRI machine is operated within FDA guidelines so the potential for inducing PNS is low. If they feel dizzy or light-headed, we will have them get up slowly from the scanner. Because the strong electromagnetic fields can move metal objects and cause heating, there is a risk that loose objects (jewelry, keys) outside the body could be accelerated by the magnetic field and strike them, causing them injury. We keep the environment around the MRI scanner completely free of loose metal objects that could be moved by the magnetic field, and we will make sure that they have no metal on the body that could be affected by the MRI scanner.

We will also ask them questions and have them complete an MRI screening form to make sure that they have no metal inside the body that would cause them harm during the MRI scan.

Further, they will not be enrolled in the study if they: 1) have a heart pacemaker, 2) are pregnant, 3) have had brain surgery for an aneurysm (weakening of the blood vessels), 4) have had major surgery within the past 4 weeks, 5) have a neurostimulator (a device that sends precise electrical pulses to the stomach), 6) have metal fragments in or near the eye or brain, or 7) are claustrophobic (fear of being in closed spaces).

As with any research study, there may be additional risks that are unknown or unexpected.

**Incidental MRI and/or behavioral findings.** Any MRI scans that appear to have potential clinical abnormality will be forwarded to a neuroradiologist, and if confirmed abnormal, the findings will be communicated to the study investigator, who would notify the participant and, with permission, be forwarded to the participant's primary care physician. Further referrals to appropriate clinicians would be made as appropriate.

